8.11.5 Critical Procedures Based on Study Objectives: Timing of Procedure

For this study, the timely and accurate collection and recording of AEs, along with blood samples for anti-SARS-CoV-2 spike serum neutralizing antibody titers (PNA) and anti-SARS-CoV-2 spike IgG titers (ELISA) are the critical procedures.

At any postdose time point, the blood sample for PNA and ELISA titers needs to be collected as close to the exact time point as possible. All other procedures should be completed as close to the prescribed/scheduled time as possible. Study procedures can be performed prior or after the prescribed/scheduled time.

The order of priority can be changed during the study with joint agreement of the investigator and the Sponsor Clinical Director.

Any nonscheduled procedures required for urgent evaluation of safety concerns take precedence over all routine scheduled procedures.

The following variance in procedure collection times will be permitted.

Vaccination Day Postdose procedure of panels A and B may be obtained within approximately 8 hours [± 15 min] for Day 1 and Day 57. Vaccination Day Postdose procedure for the sentinel participants in Panel E may be obtained within approximately 8 hours [± 15 min] for Day 1. Vaccination day (D1, D57, D169) postdose procedure may be obtained within approximately 1 hour [± 15 min] for all other panels and remaining participants of panel E. Day 2, Day 58 and Day 170 (for 2-dose panels only) evaluations can occur any time the day after dosing (approximately 18 to 30 hours post-dose)

Day 8 evaluations can occur ± 24 hours (approximately Day 7 to Day 9 postdose)

Site visit windows as outlined for Two dose Panels in [Table 7](#) and Single dose Panels [Table 8](#).

Table 7 Two Dose Panels (Panels A-B, F and I-J) Site Visit Windows

Site Visit	Visit Window
Day 1	No variance
Day 2	On the day after Day 1 visit
Day 8	± 1 day
Day 15	± 1 day
Day 29	± 3 days
Day 57/Day 169	± 3 days
Day 58, Day 170	On the day after Day 57 or Day 169
Day 71	± 1 day
Day 85, Day 197	± 3 days
Day 115, Day 365	± 7 days
Day 211	± 14 days
Day 422, Day 534	± 14 days

Table 8 Single Dose Panels (Panels C-E, G-H) Site Visit Windows

Site Visit	Visit Window
Day 1	No variance
Day 2	On the day after Day 1 visit
Day 8	± 1 day
Day 15	± 1 day
Day 29	± 3 days
Day 57	± 3 days
Day 85	± 3 days
Day 115	± 7 days
Day 211	± 14 days
Day 365	± 14 days

8.11.6 Study Design/Dosing/Procedures Modifications Permitted Within Protocol Parameters

This is a Phase 1/Phase 2 assessment of V591 in humans, and the safety profile of the vaccine is still being elucidated. This protocol is written with some flexibility to accommodate the inherent dynamic nature of early phase clinical studies. Modifications to the dose, dosing regimen, and/or clinical or laboratory procedures currently outlined may be required to achieve the scientific goals of the study objectives and/or to ensure appropriate safety monitoring of the study participants. As such, some alterations from the currently outlined dose and/or dosing regimen may be permitted based on newly available data, but the maximum doses may not exceed those currently outlined in the protocol.

- Repeat of or decrease in the dose of the study intervention administered in any given panel
- Interchange of doses between panels
- Entire panel(s) may be omitted, or the number of participants in each panel may be decreased
- Modification of the vaccination interval between the 1st and 2nd vaccination (for 2-dose panels only)
- Modification of the sample processing and shipping details based on newly available data
- Modification of the immunogenicity sampling schedule, including omitting timepoints
- Addition of a siDMC review
- Addition of Safety Phone Call Follow-ups
- Clinic in-person visit may be replaced by telephone, video or home visit using a site staff or a nursing service if circumstance do not support an in-person site visit.

The safety and immunogenicity sampling scheme currently outlined in the protocol may be modified during the study based on newly available data. If indicated, these collected samples may also be assayed in an exploratory manner for metabolites and/or additional pharmacodynamic markers.

Up to additional 50 mL of blood may be drawn for safety and/or immunogenicity analyses. The total blood volume withdrawn from any single participant will not exceed the maximum allowable volume during his/her participation in the entire study (Appendix 8).

The timing of procedures for assessment of safety procedures (eg, vital signs, ECG, safety laboratory tests, etc.) may be modified during the study based on newly available data.

Additional laboratory safety tests may be added to blood samples previously drawn to obtain additional safety information. These changes will not increase the number of study procedures for a given participant during his/her participation in the entire study.

It is understood that the current study may employ some or none of the alterations described above. Any non-substantial alteration made to this protocol to meet the study objectives must be detailed by the Sponsor in a letter to the Study File and forwarded to the investigator for retention. All substantial changes to the protocol will be submitted to the regulatory authorities and ethics committees accordingly for evaluation and approval before implementation. .

9 STATISTICAL ANALYSIS PLAN

This section outlines the statistical analysis strategy and procedures for the study. If, after the study has begun, but prior to any unblinding, changes are made to primary and/or key secondary hypotheses, or the statistical methods related to those hypotheses, then the protocol will be amended (consistent with ICH Guideline E-9). Changes to exploratory or other non-confirmatory analyses made after the protocol has been finalized, but prior to unblinding, will be documented in a supplemental SAP (sSAP) and referenced in the Clinical Study Report (CSR) for the study. Post hoc exploratory analyses will be clearly identified in the CSR.

9.1 Statistical Analysis Plan Summary

Key elements of the statistical analysis plan are summarized below; the comprehensive plan is provided in Sections 9.2-9.9.

Study Design Overview	A Phase 1/Phase 2, Randomized, Double-Blind, Placebo-Controlled, Dose-Ranging Trial to Evaluate the Safety, Tolerability and Immunogenicity of V591 in Healthy Younger and Older Participants
Treatment Assignment	260 participants (10 in Part 1 younger sentinel cohort, 100 in Part 2A younger cohort and 150 in Part 2B older cohort) will participate in the study that will include a total of 4 dose-levels and 12 Panels. Under each panel, participants will be randomized to receive V591 or placebo in a 4:1 ratio.
Analysis Populations	Safety: All Participants as Treated (APaT) Immunogenicity: Per-Protocol (PP)
Primary Endpoint(s)	
• Solicited injection site AEs from Day 1 through Day 5 after any study intervention• Solicited systemic AEs from Day 1 through Day 14 after any study intervention• Unsolicited AEs from Day 1 through Day 28 after any study intervention• SAEs and MAAEs from Day 1 throughout the duration of study
Key Secondary Endpoints	
• Anti-SARS-CoV-2 spike serum nAb as measured by PNA• Anti-SARS-CoV-2 spike IgG as measured by ELISA

Statistical Methods for Key Safety Analyses
	
For the Tier 2 endpoints, 95% CIs will be provided for between-treatment differences in the percentage of participants with events; these analyses will be performed using the Miettinen and Nurminen method (1985) [Miettinen, O. and Nurminen, M. 1985].


Statistical Methods for Key Efficacy/Immunogenicity/ Pharmacokinetic Analyses
	
The geometric mean ratios and 95% CIs of the anti-SARS-CoV-2 spike serum nAb GMTs will be calculated using a cLDA method proposed by Liang and Zeger (2000) [Liang, K-Y and Zeger, S. L. 2000]. In this model, the response vector consists of the log-transformed prevaccination and postvaccination antibody titers. The repeated measures model will include terms for time, the interaction of time-by-vaccination group (with a restriction of the same baseline mean across groups). The treatment difference in terms of a geometric mean ratio at a given post-vaccination time point will be estimated and tested from this model. The term for time will be treated as a categorical variable. An unstructured covariance matrix will be used to model the correlation among repeated measurements. This model allows the inclusion of participants who are missing either the baseline or postbaseline measurements, thereby increasing efficiency. A similar statistical approach will be used to evaluate the anti-SARS-CoV-2 spike IgG responses.


Interim Analyses
	
Up to two interim analyses may be performed on safety and immunogenicity data through at least Day 29. In order to trigger the first interim analysis at least 75% of study participants per Panel in at least 6 Panels must have completed their Day 29 visit. In order to trigger the second interim analysis at least 75% of study participants per Panel in at least 10 Panels must have completed their Day 29 visit.
 
An interim analysis may be performed on safety and immunogenicity data through at least Day 85 for Panels A, B, I, and J. To trigger this interim analysis at least 75% of these Panel’s participants must have completed their Day 85 visit. A minimum percentage of participants from other study Panels is not required for this interim analysis, though all available data will be included.
 
An interim analysis may be performed on safety and immunogenicity data through at least Day 197 for Panels K and L. To trigger this interim analysis at least 75% of these Panel’s participants must have completed their Day 197 visit. A minimum percentage of participants from other study Panels is not required for this interim analysis, though all available data will be included.
 
These interim immunogenicity analyses will include all available nAb PNA and IgG ELISA data.
 
Results of the interim analysis will be provided to the unblinded siDMC.

Multiplicity
	
No multiplicity adjustment is planned.

Sample Size and Power
	
Safety: Section 9.9.1 provides information about the ability of this study to estimate the incidence of AEs within the V591 group as well as differences between V591 and Placebo.
 
Immunogenicity: This is a descriptive study and there are no hypotheses to be evaluated. This study will randomize approximately a total of 208 participants into 4 different dose-levels of the V591 group and 52 participants into the placebo group. Section 9.9.2 provides information about the expected variability of the GMT ratios given the sample size.

9.2 Responsibility for Analyses

The statistical analysis of the data obtained from this study will be the responsibility of the Clinical Biostatistics department of the Sponsor.

This study will be conducted as a double-blind study. The official, final database will not be unblinded until medical/scientific review has been performed, protocol deviations have been identified, and data have been declared final and complete. Section 6.3.3 specifies the roles and responsibilities of the site and Sponsor personnel who will be unblinded during the study.

The Clinical Biostatistics department will generate the randomized allocation schedule(s) for study treatment assignment.

Blinding details related to the planned interim analyses are described in Section 9.7.

9.3 Hypotheses/Estimation

Objectives and hypotheses of the study are stated in Section 3.

9.4 Analysis Endpoints

Analysis endpoints of safety and immunogenicity are listed below.

9.4.1 Safety Endpoints

The safety analysis endpoints include:

Solicited injection-site AEs from Day 1 through Day 5 after study intervention

Solicited systemic AEs from Day 1 through Day 14 after study intervention

Unsolicited AEs from Day 1 through Day 28 after study intervention

The broad AE categories consisting of any AE and any vaccine-related AE from Day 1 through Day 28 after study intervention

The broad AE categories consisting of any SAE, any vaccine related SAEs, and death from Day 1 through the duration of participation in the study

The broad AE categories consisting of any MAAE and any ECI (event of clinical interest) from Day 1 throughout the duration of the study.

Maximum temperature measurements meeting the Brighton Collaboration cut points from Day 1 through Day 14 after study intervention

Safety laboratory results, vital signs, and physical exam findings as described in the SoA

9.4.2 Immunogenicity Endpoints

The immunogenicity analysis endpoints include:

Anti-SARS-CoV-2 spike serum nAb as measured by PNA

Anti-SARS-CoV-2 spike IgG as measured by ELISA

PBMCs stimulated with SARS-CoV-2 Spike peptides for characterization of cell mediated immunity and serum to characterize the immune response to V591

Anti-SARS-CoV-2 N-protein IgG responses as measured by immunoassay

9.5 Analysis Populations

9.5.1 Safety Analysis Populations

Safety analyses will be conducted in the All Participants as Treated (APaT) population, which consists of all randomized participants who received at least one dose of study intervention. Participants will be included in the treatment group corresponding to the study intervention they received for the analysis of safety data using the APaT population. This will be the treatment group to which they are randomized except for participants who receive an incorrect dose of study vaccine or placebo; such participants will be included in the treatment group corresponding to the study treatment actually received. In the 2-dose panels, safety parameters for cross-treated participants (ie, those who received vaccinations of both V591 and Placebo) will be summarized separately.

9.5.2 Immunogenicity Analysis Populations

The Per-Protocol (PP) population will be used for the analysis of immunogenicity data in this study. The PP population consists of all randomized participants without deviations from the protocol that may substantially affect the results of the immunogenicity endpoint. Potential deviations that may result in the exclusion of a participant from the PP population for all immunogenicity analyses include:

- Failure to receive any study vaccine at Day 1
- Failure to receive the correct dose of study vaccine at Day 1
- Receipt of prohibited medication or prohibited vaccine prior to the Day 1 blood sample collection

Additional deviations that may result in the exclusion of a participant from the PP population for specific immunogenicity analyses at a particular timepoint include:

- Collection of blood sample outside of the pre-specified window (as described in Section 1.3)

- Receipt of prohibited medication or prohibited vaccine prior to a blood sample collection
- Failure to receive the second dose of V591 or placebo according to vaccination schedule (for 2-dose panels only)

The final determination on protocol deviations, and thereby the composition of the PP population, will be made prior to the final unblinding of the database. Participants will be included in the vaccination group to which they are randomized for the analysis of immunogenicity data using the PP population. Determinations on protocol deviations will be made by blinded study team members prior to the planned interim analyses (Section 9.7) and prior to the final unblinding of the database. Participants will be included in the vaccination group to which they are randomized for the analysis of immunogenicity data using the PP population.

A supportive analysis using the Full Analysis Set (FAS) population will also be performed for the key secondary immunogenicity analysis endpoints. The FAS population consists of all randomized participants who received at least 1 vaccination and have at least 1 serology result. Participants will be included in the vaccination group to which they are randomized for the analysis of immunogenicity data using the FAS population.

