Urinalysis	X				X	X	X	X	X				X	Section 8.3.7 and Appendix 2
Chemistry	X				X	X	X	X	X				X	Section 8.3.7 and Appendix 2
Screening and SARS-CoV-2 Test														
SARS-CoV-2 PCR	X													Appendix 2
Immunogenicity														
Serum Collection for Neutralizing Antibodies by PNA		X				X	X	X	X	X	X	X	X	Leftover main study serum samples to be stored for FBR
Serum Collection for Total Anti-spike IgG and Total Anti-N IgG Antibodies by ELISA		X				X	X	X	X	X	X	X	X	Leftover main study serum samples to be stored for FBR
Serum collection for Immunological Assessments (Panels C, D, G, and H only)		X			X									Leftover main study serum samples to be stored for FBR
PBMC collection for Immunological Assessments (Panels C, D, G, and H only)		X					X							Leftover main study PBMC samples to be stored for FBR
Biomarkers														
Blood (DNA) for Future Biomedical Research		X												Section 8.9 Collect from enrolled participants only.

1-dose Panels C-E and G-H													
	Screening	Study Day										Post-Study	Notes
Scheduled Hour, Day, Week, etc.	Screening -28 to -1 ^b	Day 1 Pre-dose	1	2 ^a	8±1	15±1	29±3	57±3	85±3	115±7	211±14	365±14	Section 8.11.5 Details on variance in procedure collection times

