4.2.1.3 Exploratory Endpoints

In accordance with regulatory guidance, this trial will endeavor to identify potential exposures and infections by SARS-CoV-2 amongst study participants. However, this clinical trial is not intended to interfere with local health practices and regulations regarding the management of confirmed or suspected SARS-CoV-2 infections. Study participants will be tested as appropriate according to local regulations and will receive any required medical care within their existing healthcare systems, please refer to Section 8.3.7 for further details.

Additional exploratory endpoints will include the follow assessments to assess the potential exposure to and infection by SARS-CoV-2 amongst study participants without potentially disrupting medical care:

- SARS-CoV-2 N protein specific antibody up to Study Day 534 as assessed by immunoassay. As the SARS-CoV-2 N protein is not included in the vaccine, infections in study participants seroconversion will identify asymptomatic and paucisymptomatic SARS-CoV-2 over the entire course of the study.
- Any laboratory confirmed diagnosis of SARS-CoV-2 infection (PCR or antigen based) and any resulting clinical sequelae will be reported as an ECI in study participants throughout the duration of the study.
- Known exposure to a confirmed case of active SARS-CoV-2, defined as individual who has had close contact (< 1.5 meters for ≥ 15 minutes), will be reported as an ECI in study participants throughout the duration of the study.

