As participants in Panel A, Panel B, and the first 5 subjects in Panel E will be amongst the first to receive doses of $1 \cdot 10^5$ TCID₅₀, $1 \cdot 10^6$ TCID₅₀, and $1 \cdot 10^7$ TCID₅₀ V591 respectively, they will be required to be seronegative for SARS-CoV-2 as an additional precaution. Participants in the rest of the study will not be screened by serology for SARS-CoV-2 and thus will not be required to be seronegative for enrollment.

Doses of $1 \cdot 10^5$ TCID₅₀ and $1 \cdot 10^6$ TCID₅₀ will also be the only dose levels administered to older participants after they have been assessed to be well tolerated in younger adults based on data from this study or the COVID-19-101 study as outlined in Section 4.1. These are doses that are most likely to be both well tolerated and immunogenic in this population, and it is intended to only administer V591 doses that are generally well tolerated and anticipated to elicit an immune response against SARS-CoV-2 in older participants. Two dose regimens of V591 will be given either 8 or 24 weeks apart in Panels of adults > 55 years of age. As older adults have historically demonstrated weaker responses to vaccines [Weinberger, B. 2012], 2 dose regimens of V591 with wider intervals than the 4 week interval in the COVID-19-101 study will be evaluated in an effort to identify a regimen of V591 that displays enhanced immunogenicity in older adults. This design will minimize the risks to older participants while efficiently obtaining immunogenicity data in this older population that is at greatest risk for severe COVID-19 disease.

In an previous Phase 1 study, MV-CHIK 101, that explored doses ranging from $1.5 \cdot 10^4$ to $3 \cdot 10^5$ TCID₅₀ of MV-CHIK in healthy adults, Doses of $7.5 \cdot 10^4$ and $3 \cdot 10^5$ TCID₅₀ MV-CHIK were generally immunogenic after a single vaccination, while the lower dose of $1.5 \cdot 10^4$ TCID₅₀ required 2 doses for comparable immunogenicity. Based on this clinical data, it is anticipated that a single dose of V591 greater than $7.5 \cdot 10^4$ TCID₅₀ may provide adequate immunogenicity after a single dose. Thus a single dose of $1 \cdot 10^5$ TCID₅₀ will be the lowest dose administered as a single dose regimen in this trial.

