5.2 Exclusion Criteria

The participant must be excluded from the study if the participant:

Medical Conditions

1. Is currently actively infected with SARS-CoV-2 (confirmed by PCR).
2. Has prior medical history of confirmed SARS-CoV-2 infection or known exposure to an individual with confirmed COVID-19 disease or SARS-CoV-2 infection within the past 2 weeks. With the exception of the sentinel participants (Panel A, Panel B, and the first 5 subjects of Panel E), study participants will not be screened for enrollment by SARS-CoV-2 serology, allowing those who may have had a prior asymptomatic SARS-CoV-2 infection to be enrolled.
3. Has a history of severe adverse reactions to vaccine administration, including anaphylaxis and related symptoms, such as urticaria, respiratory difficulty, angioedema and abdominal pain to vaccines, or history of known or suspected allergic reaction likely to be exacerbated by any component of the COVID-19 vaccine.
4. Is currently (or highly suspected to be) immunocompromised, including anticipating the need for systemic immunosuppressive treatment within the next 6 months or 12 months for 2-dose Day 1 Day 169 panels or has been diagnosed or highly suspected as having a congenital or acquired immunodeficiency, HIV infection, lymphoma, leukemia, systemic lupus erythematosus (SLE), rheumatoid arthritis, juvenile rheumatoid arthritis (JRA), inflammatory bowel disease, or other autoimmune condition that could impact the immune response or the safety of the study vaccine.
5. Has clinically significant thrombocytopenia or other coagulation disorder contraindicating intramuscular vaccination or repeated venipuncture.
6. *Had a recent febrile illness (defined as oral or tympanic temperature $\geq 100.4^{\circ}\text{F}$ [$\geq 38.0^{\circ}\text{C}$] within a week before receiving the first study vaccination.
7. Has history or current evidence of any condition, therapy, laboratory abnormality, or other circumstance that might expose the participant to risk by participating in the study, confound the results of the study or interfere with the participant's participation for the full duration of the study.
8. Has a history or presence of clinically significant pulmonary disorders (e.g. COPD, etc.), or asthma.

9. Has a history of confirmed SARS-CoV-1 or MERS.
10. Has a history of or a current clinically significant medical condition that puts or may put a participant at increased risk for severe SARS-CoV-2 disease.

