This clinical trial is not intended to interfere with local health practices and regulations regarding the management of confirmed or suspected SARS-CoV-2 infections or COVID-19 disease. The main role of the Investigator to help study participants to receive all appropriate

medical care according to local health practices and regulations. Study participants may be tested as appropriate according to local regulations and will receive any required medical care within their existing healthcare systems. However if a subject is not administered a nasopharyngeal PCR test for SARS-CoV-2 according to local regulations and the Investigator feels it is warranted, then they may directly arrange for SARS-CoV-2 PCR testing as available by nasopharyngeal swab.

If a subject is suspected/diagnosed with an actual COVID-19 infection they will not receive any subsequent study vaccination but should endeavor to perform all visits for safety follow-up that they are safely able to attend in person as allowed according to local regulations.

Exposure to known SARS CoV-2 infected patients and SARS-CoV-2 infection, and COVID-19 disease, will be captured as ECIs as documented in Section 8.4.7.

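### The Per-Protocol immunogenicity set has no rule for SARS-CoV-2 infection, so antibody from on-study or unrecognised prior infection is counted as response in both arms

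*Combined protocol and SAP*

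**What the plan says.** Section 9.5.2 gives the general rule: "The PP population consists of all randomized participants without deviations from the protocol that may substantially affect the results of the immunogenicity endpoint". Two lists of deviations follow.

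- **All timepoints:** no Day 1 vaccine, a wrong Day 1 dose, or "Receipt of prohibited medication or prohibited vaccine prior to the Day 1 blood sample collection".
- **Particular timepoints:** a sample outside its window, a prohibited medication or vaccine before that sample, or "Failure to receive the second dose of V591 or placebo according to vaccination schedule".

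Neither list names PCR-confirmed infection, anti-N status or serostatus at baseline.

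Prior unrecognised infection is permitted. Exclusion criterion 2 in Section 5.2 limits serology screening to the sentinels, "allowing those who may have had a prior asymptomatic SARS-CoV-2 infection to be enrolled". Section 4.2.6 agrees: outside the sentinels there is no serology screen and no need for a negative result. Infection during the study is recorded as an event of clinical interest (Sections 4.2.1.3 and 8.4.7), not as a deviation. Section 8.3.7 adds one consequence for dosing: "If a subject is suspected/diagnosed with an actual COVID-19 infection they will not receive any subsequent study vaccination".

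Section 4.2.1.3 states why anti-N tells infection from vaccination: "As the SARS-CoV-2 N protein is not included in the vaccine". The three schedules in Section 1.3 carry a row for "Serum Collection for Total Anti-spike IgG and Total Anti-N IgG Antibodies by ELISA" at Day 1 predose and at every later anti-spike visit. Anti-N nevertheless serves only an exploratory objective in Section 3, and Section 8.2.4 leaves open whether the exploratory assays are run.

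The model in Section 9.6.2 has terms for time and time-by-group only. The FAS takes everyone with one vaccination and one serology result.

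**The concern.** Infection raises anti-spike IgG and neutralising antibody, as the vaccine is meant to do. Under the written rules, serum carrying infection-derived antibody enters the V591/placebo ratio, the group GMTs and GMCs, and the fold-rises as if it were vaccine response or background. The study was run during the pandemic, and 245 of 260 participants had no serology at entry.

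Three consequences have to be kept apart:

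- **Ratio.** If infected people gain little more from vaccine, equal infection in both arms pulls the ratio towards 1. Unequal infection, by chance, can push it either way.
- **Group GMTs.** These have no placebo correction. Any infection raises the placebo GMT, and raises a V591 GMT when infection titres exceed vaccine titres. The Amendment 04 rationale suggests they do, since it reports V591 responses below those after natural infection.
- **Fold-rises.** Only infection after Day 1 inflates these. A participant already positive at Day 1 has a high denominator and would tend to lower the group fold-rise.

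**Working it through.** **Inputs from the documents**
- Allocation 4:1 (Sections 1.1, 6.3.1); 208 V591 and 52 placebo (Section 9.1).
- 84 participants at each of 10⁵ and 10⁶ TCID₅₀ on Day 1 (Table 12); 20 V591 recipients per non-sentinel panel (Tables 3 and 4).
- 85% evaluable at Day 29 and SD of ln titre from 1.0 to 2.0 (Section 9.9.2).
- Seronegativity required for 5 + 5 + 5 = 15 sentinels, leaving 260 − 15 = 245 untested.

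**Inputs not in the documents (assumed)**
- Infected share q = 5% to 20%.
- Fold-rise from infection F = 10 to 30 for the intervals, and 10 to 50 for the single-infection scenario.
- Infected people gain nothing further from vaccine.

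**1. The plan's own figure.** Table 13 uses ratio × exp(± t × SD × √(1/n₁ + 1/n₀)). With n₁ = 0.85 × 84 ≈ 71, n₀ = 0.85 × 57 ≈ 48, t on 117 df = 1.980 and SD 1.0, the exponent is 1.980 × 0.1869 = 0.370. A ratio of 1.5 gives 1.04 to 2.17, as printed; all 12 cells reproduce to within 0.005. The 57 does not match the 52 placebo recipients in Section 9.1 and Tables 3 and 4, so the steps below use 0.85 × 52 ≈ 44.

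**2. Interval without infected serum.** 71 v 44, SD 1.0: exponent 1.981 × 0.1919 = 0.380. A ratio of 3.0 has CI 2.05 to 4.39.

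**3. Equal infection in both arms.** On the log scale the expected ratio is R^(1−q). The variance becomes SD² + q(1−q)(ln F)² in placebo and SD² + q(1−q)(ln(F/R))² in V591.

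| q | True 3.0 becomes | CI, F = 10 | CI, F = 30 |
|---|---|---|---|
| 5% | 3^0.95 = 2.84 | 1.88–4.29 | 1.80–4.48 |
| 10% | 3^0.90 = 2.69 | 1.73–4.18 | 1.61–4.49 |
| 20% | 3^0.80 = 2.41 | 1.49–3.90 | 1.33–4.38 |

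A true ratio of 1.5 at q = 5% becomes 1.5^0.95 = 1.47. Its lower limit falls from 1.03 to 0.97 (F = 10) or 0.92 (F = 30).

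**4. Whether baseline adjustment removes this.** A baseline-adjusted regression was simulated as a stand-in for the constrained longitudinal model (71 v 44, q = 10%). With infection before Day 1, a true 3.0 came out at 2.71 (F = 10) and 2.70 (F = 30), with log-scale SE about 0.17. With infection after Day 1 it came out at 2.69 and 2.70, with SE 0.19 and 0.23. Adjustment recovers precision for baseline positives but leaves the pull towards 1.

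**5. Adverse imbalance.** One infection among 44 placebo recipients and none in V591 multiplies the ratio by F^(−1/44). This is 0.949 at 10-fold (a 5.1% cut) and 0.915 at 50-fold (an 8.5% cut).

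**6. One dose group.** With 0.85 × 20 = 17 evaluable, one infection giving a 10-fold excess multiplies that group's GMT by 10^(1/17) = 1.145.

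**7. Cost of exclusion.** At q = 5% the groups become 67 v 42. The estimate stays at 3.0 with CI 2.03 to 4.43, against 2.05 to 4.39 in step 2.

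**The case against.** The case for leaving the plan alone has several parts.

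- **The lists are open.** Both describe deviations that may lead to exclusion. They are still lists of deviations, so removing infected serum under them would be an unplanned judgement.
- **Placebo controls for exposure.** Section 4.2.2 says so, and 4:1 allocation means most infections would fall in V591. This rules out treating all-in-placebo figures as expected. It does not make infection cancel, because the ratio is still pulled to R^(1−q).
- **Some infections already leave the set.** A participant diagnosed before dose 2 gets no dose 2, eligibility is reviewed again then (Section 7.1), and the missed-dose item can remove later samples. Prohibited treatment could remove a few more. This stands for recognised infection in two-dose panels only.
- **Entry is restricted.** PCR positives, confirmed prior infection, recent known exposure and high-risk occupations are excluded. What remains at baseline is unrecognised infection, which the sponsor chose to allow. Restricting the main summary to anti-N negatives is therefore partly a choice of estimand, so baseline positives should be reported and not dropped.
- **Consequences are limited.** The study is descriptive, and Table 13's intervals are wide compared with a 5% to 10% shift. This lowers the urgency.

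A reader might infer a 21% to 32% cut at Day 85, from one infection among 12 × 0.85 ≈ 10 placebo recipients at 10- to 50-fold. The documents do not support that as an expected effect. It puts the only infection in placebo, uses an evaluable rate stated for Day 29 only, and ignores the missed-dose route. A bias that keeps growing at later visits is also unsupported, because Section 8.11.4 under Amendment 04 ends immunogenicity serum collection at the final visit.

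**Conclusion.** The gap is real and its expected size is modest. The Per-Protocol set, the model and the FAS all keep infection-derived titre, and no analysis by serostatus or infection is described. Under equal infection with no further vaccine gain in infected people, the ratio shrinks by about 5% at q = 5% (3.0 to 2.84) and 10% at q = 10% (3.0 to 2.69). One placebo infection at Day 29, as an adverse case, cuts it by 5.1% to 8.5%. These sizes rest on assumed infection rates and fold-rises; the direction in any one dataset depends on where infections fall.

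A reader might infer that retained infected serum explains the sponsor's decision to stop for weak immunogenicity. The documents do not support this. They do not say which analysis set informed that decision, and infected serum would raise V591 GMTs towards natural-infection levels, not lower them.

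The point is worth acting on because the final analysis is still planned and the needed serum is already scheduled. It concerns secondary endpoints and does not touch the primary safety objective.

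**What to change.** In Section 9.5.2:

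- Add to the timepoint-specific Per-Protocol exclusions any sample from the first PCR-confirmed SARS-CoV-2 infection or anti-N seroconversion onward, dated from the first positive result.
- Present the Per-Protocol model results, GMTs/GMCs and fold-rises for participants who are anti-N negative at Day 1, and summarise baseline-positive participants separately.
- Keep all samples in the supportive FAS, so the effect of the exclusion can be seen.

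In Section 8.2.4, make the anti-N assay mandatory on Day 1 and comparison-visit serum, with results available before the blinded Per-Protocol determination. Anti-N is not vaccine-encoded, so blinded staff can apply the rule without learning assignment.

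**Cost.** SAP wording, an assay that is currently optional and must be run in time, and a few lost samples (71 v 44 becomes 67 v 42 at q = 5%). The rule conditions on a post-randomisation event that vaccination could affect, and the FAS is the check on that. Infections that neither PCR nor anti-N detects stay in.
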